9.2.3 Study visits

Baseline visit:

No data collection for study purposes must be performed unless the patient has consented to participate in the study. Once the patient has signed the informed consent form, the patient is considered to be enrolled in the study and patient details should be recorded on the enrolment log.

The following procedures will be performed at the baseline visit:

- Sign informed consent form
- Review of inclusion and exclusion criteria
- Collection of demographic data: age, gender,
- Collection of concomitant diseases/co-morbidities in the medical history and at baseline
- Collection of current concomitant therapies
- Weight
- Creatinine Clearance: serum creatinine value (if available) to be entered on eCRF, Creatinine Clearance according to Cockcroft-Gault formula to be automatically calculated CHA2DS2-VASc and HAS-BLED score calculation in eCRF
- For Cohort A only: duration of previous treatment with VKA to be documented
- For Cohort A only: reasons for switch to Pradaxa[®] to be documented
- Documentation of Pradaxa[®] dosing
- Patient will be asked to complete the following patient related questionnaires:
 - PACT-Q2 (Cohort A only)
 - PACT-Q1 (Cohort B only)
- Treatment with Pradaxa[®] or VKA will be initiated

Initiation period:

During a routine practice visit occurring at 30 – 45 days after initiation of treatment, the following assessments will be documented:

- Current dosing of Pradaxa[®] and reasons for dose change (if applicable)
- New or changed concomitant diseases/co-morbidities
- Changes in concomitant therapies
- Creatinine Clearance: serum creatinine value (if available) to be entered on eCRF, Creatinine Clearance according to Cockcroft-Gault formula to be automatically calculated
- Weight (if needed for creatinine clearance calculation at V2)
- Collection and reporting of ADR (serious and non-serious), fatal AEs, or pregnancies (if applicable)
- Reasons for Pradaxa[®] or VKA discontinuation (if applicable)
- Patients will be asked to complete the PACT-Q2 questionnaire

Continuation period:

During a routine practice visit occurring at 150-210 days after initiation of treatment, the following assessments will be documented:

- Current dosing of Pradaxa[®] and reasons for dose change (if applicable)
- New or changed concomitant diseases/co-morbidities
- Changes in concomitant therapies
- Creatinine Clearance: serum creatinine value (if available) to be entered on eCRF, Creatinine Clearance according to Cockcroft-Gault formula to be automatically calculated
- Weight (if needed for creatinine clearance calculation at V3)
- • Collection and reporting of ADR (serious and non-serious), fatal AEs, or pregnancies (if applicable)
- Reasons for Pradaxa[®] or VKA discontinuation (if applicable)
- Patients will be asked to complete the PACT-Q2 questionnaire

With this visit, the patient's participation in the study will be completed.

Description and justification of patient questionnaires:

PACT-O[®]:

The PACT-Q was developed as a means to investigate patients' satisfaction with anticoagulant treatment and treatment convenience in patients with deep venous thrombosis (DVT), pulmonary embolism (PE) or atrial fibrillation (AF) (R15-1314; R15-1316). The PACT-Q is a self-administered questionnaire. It can be completed in about ten minutes. No specific training is required to complete this document.

The original PACT-Q consists of two parts and contains 27 items:

- The PACT-Q1 is composed of a single dimension (7 items), covering the expectations of patients regarding their anticoagulant treatment, and is to be administered before treatment initiation.
- The PACT-Q2 is composed of three dimensions covering: convenience (11 items), burden of disease and treatment (2 items), and anticoagulant treatment satisfaction (7 items). The PACT-Q2 is to be administered to patients once treatment is ongoing.

Patients will either be switched from VKA treatment to Pradaxa[®] (cohort A) or newly initiated on Pradaxa[®] or VKA (cohort B).

- Pradaxa[®] 110 mg hard capsules
- Pradaxa[®] 150 mg hard capsules
- Vitamin K antagonist

9.2.3.1 Treatments

Pradaxa[®] 110 mg and Pradaxa[®] 150 mg hard capsules contain Dabigatran etexilate (active moiety: Dabigatran).

Patients will receive daily dose of Pradaxa[®] according to the approved country label and physician's discretion.

The choice of vitamin K antagonist and the appropriate dosing is in the discretion of the physician. The applicable approved country label of the chosen treatment should be referred to.

9.2.3.2 Concomitant medications and restrictions

All concomitant medications are prescribed based on the underlying medical condition and upon the discretion of the treating physician. No treatment will be withheld from the patients. Any prescription is in the responsibility of the treating physician.

9.2.3.3 Representativeness of the study population

Inclusion and exclusion criteria have been limited to the respective approved country label of Pradaxa[®] and VKA. Therefore the patient population recruited in this non-interventional study can be seen as representative for patients receiving an oral anticoagulation for stroke prevention in non- valvular atrial fibrillation.

9.2.4 Study discontinuation

Boehringer Ingelheim reserves the right to discontinue the study overall or at a particular study site at any time for the following reasons:

1. Failure to meet expected enrolment goals overall or at a particular study site
2. Violation of Good Clinical Practice (GCP) (as applicable), the study protocol, or the contract by a study site or investigator, disturbing the appropriate conduct of the study
3. Any other administrative reasons

The investigator / the study site will be reimbursed for reasonable expenses incurred in case of study termination (except in case of the second reason).

9.3 VARIABLES

9.3.1 Variables for objective 1

Primary outcome

For Cohort A (switcher):

- Mean PACT-Q2 scores at second and last assessment compared to baseline assessment

For Cohort B (newly initiated):

- Mean PACT-Q2 scores at second and last assessment between treatment groups

Secondary outcome:

For Cohort A (switcher):

- Mean PACT-Q2 score at last assessment compared to second assessment

For Cohort B (newly initiated):

- Description of PACT-Q1 items at baseline

9.3.2 Variables for objective 2

Primary outcome:

Characterization of patients from both cohorts according to

- Age
- Gender
- CHA2DS2-VASc score ([R10-5332](#))
- HAS-BLED score (modified HAS-BLED for newly initiated patients) ([R10-6394](#))
- Kidney function (creatinine clearance)
- Stroke- and/or bleeding related risk factors in medical history and at baseline
- Co-morbidities
- Concomitant therapies
- Dosing of Pradaxa[®]
- Duration of previous VKA treatment (for Cohort A)

9.4 DATA SOURCES

Data will be newly collected from the patient by the investigator and recorded as source data at the site, i.e. the physicians records, and entered in the eCRF by the investigator or site staff. Patients will be asked to complete the respective questionnaires during their routine visits. Patient demographic data, concomitant diseases and concomitant therapies will be completed based on the physician's records. Information on Pradaxa[®] and/or VKA dosing will be collected from physician's records. Creatinine clearance for assessment of kidney function will be calculated within the eCRF, by entering Creatinine values (from existing lab reports, if available), and weight (if applicable) to be measured by the physician or delegated site staff.

9.5 STUDY SIZE

It is planned that a total of approximately 1790 patients from 6 SEASK countries will be recruited for Cohort A and Cohort B.

Baseline demographics and disease characteristics of the patient population will be described by estimates and confidence intervals (CIs) overall (for Cohort A), by anticoagulation treatment (for Cohort B), and by additional relevant categories as specified in Section 9.7.2 and the SEAP. Categorical attributes will be estimated with the precision (i.e. width of descriptive 95% confidence interval) described in Table 9.5: 1, according to sample size and prevalence of the attribute.

Table 9.5: 1 Width of 95% confidence interval by sample size and prevalence of attribute

Prevalence of attribute		Sample size (overall or per subgroup)			
		200	500	1000	2000
10%	Expected n	20	50	100	200
	95% CI width	8.80	5.46	3.82	2.68
20%	Expected n	40	100	200	400
	95% CI width	11.53	7.20	5.05	3.55
30%	Expected n	60	150	300	600
	95% CI width	13.13	8.21	5.77	4.06
40%	Expected n	80	200	400	800
	95% CI width	13.99	8.77	6.17	4.34
50%	Expected n	100	250	500	1000
	95% CI width	14.26	8.94	6.29	4.43

* Calculations are based on the Clopper-Pearson method.

For example, for a population attribute with a prevalence of 20%, a total sample size of 1000 patients for Cohort A allows this proportion to be estimated with a precision of 5.05% (i.e. width of 95% CI).

The planned total sample size of 1790 patients is jointly determined by the following sample size assessments and additional non-statistical considerations, including feasibility assessments for the participating countries.

Due to the limited number of publications on PACT-Q2 ([R15-1314](#), [R15-1316](#), [R15-1359](#)) and the lack of information regarding the clinical meaning of changes in PACT-Q2 scores, sample size assessments are performed using standardized mean differences. In the context of this study, they represent the mean differences in PACT-Q2 scores between two assessments (for Cohort A) or between the Pradaxa® and VKA groups (for Cohort B) divided by the corresponding standard deviations. In general, a standardized effect size of 0.2 is considered a small change, 0.5 a moderate change, and 0.8 a large change.

For Cohort A, assuming a 2-sided alpha of 0.05 and a 20% loss to follow-up, a total sample size of 598 patients will provide over 80% power to detect a standardized mean difference of 0.13 in PACT-Q2 scores between two assessments.

For Cohort B, assuming a 2-sided alpha of 0.05, a 1:1 ratio of Pradaxa® and VKA patients, and a 30% loss to follow-up and matching, a total sample size of 1192 patients will provide over 80% power to detect a standardized mean difference of 0.14 in PACT-Q2 scores between the Pradaxa® and VKA groups at each assessment.

Based on results from the PREFER in AF ([R15-1312](#)) registry study, a reasonable expected standard deviation for the PACT-Q2 convenience and treatment satisfaction scores is 16. Based on this estimate, a standardized mean difference of 0.1 corresponds to an actual mean difference of 1.6 in the PACT-Q2 convenience and treatment satisfaction scores.

The PREFER in AF study ([R15-1312](#)) also reported a mean difference between patients receiving novel oral anticoagulants and those receiving VKA of -0.6 for the convenience score, and of 1.1 for the treatment satisfaction score. Since the clinical meaningfulness of such small mean differences in PACT-Q2 scores is unclear, the

current study is by design not powered to detect statistically significant differences of such small magnitudes.

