9.2.1 Study sites

Cardiologists and non-cardiologist sites regularly prescribing Pradaxa® and VKA for stroke prevention in atrial fibrillation according to the respective country approved label will participate.

Selected sites within each country should include those physicians (e.g. cardiologists, non-cardiologists) and facilities (e.g. specialist offices, hospitals, outpatient care centres etc.) that reflect the clinical practice in that country. Investigators that are currently participating in the BI registry program 1160.129 (GLORIA) are not allowed to participate in this study.

These site selection criteria will help to ensure that the patients recruited into this study will represent the patients treated within that country. After initiation, every site should include the first consecutive suitable patients where decision for switch to Pradaxa® (Cohort A) or decision for initiation on Pradaxa® or VKA (Cohort B) has been made. In consecutive sampling, every eligible patient is selected until the required sample size is enrolled. This approach helps to reduce the likelihood of selection bias.

Balance between Cohorts within each country

Within each participating country, the recruitment of patients in Cohort A and Cohort B needs to be balanced (A:B = 1:2). Within Cohort B, the patient enrolment will be controlled as well, in order to ensure that an equal amount of data will be collected of AF patients newly treated with Pradaxa® (sub-Cohort B1) or with VKA (sub-Cohort B2)

(Pradaxa[®]:VKA = 1:1). Therefore, the sponsor may have to decide to close the enrolment of patients for one of the Cohorts (or sub-Cohorts) during the recruitment period, if the other (sub) Cohort is exceeding the maximum number of enrolled patients planned for that country/site.

The decision for therapy has to be taken prior to and independently of enrolment into the study. Only after the treatment decision for the patient is taken, the investigator can check and decide if a patient can be enrolled in Cohort A or Cohort B.

Patients will then have to sign informed consent before they can take part in the non- interventional study.

A log of all patients included into the study (i.e. having given informed consent) will be maintained in the ISF at the investigational site irrespective of whether they have been treated or not.

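### The Cohort A precision example assumes 1000 patients (95% CI width 5.05 points); the planned 598 give about 6.6 points

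*Protocol*

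**What the plan says.** Protocol section 9.5 describes the precision of baseline attributes as the "width of descriptive 95% confidence interval" and tabulates it in Table 9.5: 1 for sample sizes of 200, 500, 1000 and 2000. The table footnote reads "Calculations are based on the Clopper-Pearson method".

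The worked example below the table is introduced with "for a population attribute with a prevalence of 20" per cent, and continues that "a total sample size of 1000 patients for Cohort A allows this proportion to be estimated with a precision of 5.05" per cent.

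Further on, the same section gives the size of each cohort:

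- Cohort A: "a total sample size of 598 patients will provide over 80% power to detect a standardized mean difference of 0.13", after allowing for 20% loss to follow-up.
- Cohort B: "a total sample size of 1192 patients will provide over 80% power", at a 1:1 ratio of Pradaxa to VKA.

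The planned total is 1790. Section 9.2.1 adds that within each country "the recruitment of patients in Cohort A and Cohort B needs to be balanced (A:B = 1:2"). The SAP does not repeat the example; its Introduction refers the reader to the protocol for sample size planning.

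**The concern.** Section 9.5 attaches two different total sample sizes to Cohort A, 1000 in the precision example and 598 in the power statement. Only one can be the plan, and the stated precision depends on which.

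Patient characterization is Objective 2, and this table with its example is the only statement of how precisely it will be met. Because the sentence names the cohort, a reader can fairly take 5.05 points as the planned precision for Cohort A. If the plan is 598, that figure is too favourable.

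**Working it through.** **Inputs (protocol section 9.5 unless stated)**

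- Sample size in the example: 1000; prevalence 20%; stated width 5.05 points.
- Method: Clopper-Pearson, 95%, full width.
- Cohort A sized at 598, Cohort B at 1192, total 1790.
- Cohort ratio A:B = 1:2 (section 9.2.1).

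**Formula.** For x events in n patients, the lower limit is the 0.025 quantile of Beta(x, n − x + 1) and the upper limit is the 0.975 quantile of Beta(x + 1, n − x). Width = upper − lower.

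**Step 1: reproduce the plan's figure.** With n = 1000 and x = 200 the limits are 17.56% and 22.62%, a width of 5.05 points, as stated. All 20 cells of Table 9.5: 1 reproduce to within 0.01. The calculation is sound for the sample sizes shown.

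**Step 2: which Cohort A size is the plan?**

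- 598 + 1192 = 1790, the stated total.
- 1192 / 598 = 1.99, in line with A:B = 1:2; equivalently 1790 / 3 ≈ 597.
- 598 × 0.8 ≈ 478 evaluable patients. A two-sided paired t-test at alpha 0.05 with a standardized difference of 0.13 then has 81.0% power (noncentral t), matching the claim of over 80%.
- A Cohort A of 1000 would leave 1790 − 1000 = 790 for Cohort B instead of 1192. Keeping the 1:2 ratio would need 1000 × 3 = 3000 patients.

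The plan is 598.

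**Step 3: the width at 598.** At 20% prevalence the expected count is 119.6, so both neighbouring integers are shown:

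- x = 119: 16.77% to 23.33%, width 6.56 points.
- x = 120: 16.93% to 23.50%, width 6.58 points.

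Difference from the stated figure: 6.58 − 5.05 = 1.53 points. Ratio: 6.577 / 5.054 = 1.30.

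**Step 4: other prevalences** (width in percentage points; counts at n = 598 rounded to the nearest integer)

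| Prevalence | n = 1000 (protocol table) | n = 598 | n = 600 |
|---|---|---|---|
| 10% | 3.82 | 4.98 | 4.97 |
| 20% | 5.05 | 6.58 | 6.56 |
| 30% | 5.77 | 7.49 | 7.49 |
| 40% | 6.17 | 8.00 | 7.99 |
| 50% | 6.29 | 8.17 | 8.15 |

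The intervals are about 30% wider throughout. A Cohort B treatment group of 1192 / 2 = 596 has almost the same width as Cohort A (6.58 points at x = 119).

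**The case against.** Nothing is miscalculated. The operative statement is the table, headed generically for overall or subgroup sizes; its 2000 column exceeds the whole study, so it is plainly a look-up. The disputed sentence is an example of how to read one cell. The true size appears later in the same section, and the 500 and 1000 columns (7.20 and 5.05 at 20% prevalence) bracket the correct width. The total of 1790 rests on the PACT-Q2 power assessments and feasibility; no threshold or decision depends on 5.05.

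Most of this stands as a limit on importance: it is an internal inconsistency in one illustrative sentence, without consequence for design or analysis. It does not remove the inconsistency. An example with an unattributed sample size would be harmless, but this one assigns a total to a named cohort, and that total is wrong.

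A second objection is that about 6.6 points is itself optimistic. SAP section 6.3 restricts the main analysis set to patients who took the prescribed treatment and had no important protocol violation, and creatinine clearance is available only where a serum creatinine value already exists. That is correct and should be reflected in the wording, but it widens the interval further. The 20% loss to follow-up is not the relevant reduction, because these are baseline attributes; applying it anyway (n = 478) gives about 7.37 points at 20% prevalence.

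**Conclusion.** The point holds and is minor. The example gives Cohort A a sample size that appears nowhere else in the plan and contradicts the 598 in the same section. At 20% prevalence the planned size gives a 95% interval about 6.6 points wide, 1.5 points or 30% wider than stated. This rests on the protocol's own method (Clopper-Pearson, full width) and on all 598 enrolled patients contributing data; exclusions or missing values would widen it. The table entries, the power statements, the total of 1790 and the planned analyses are unaffected.

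**What to change.** Change the example to 598 patients for Cohort A with a 95% CI width of about 6.6 percentage points at 20% prevalence, and say that this assumes all 598 are evaluable for the attribute.

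Optionally, add a column for n = 600 to Table 9.5: 1, using the widths in the last column of the table above. It would serve Cohort A and each Cohort B treatment group; the existing columns can stay.

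The cost is one sentence of protocol wording and a less favourable stated precision. Sample size, power and analysis do not change.

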9.6 DATA MANAGEMENT

A data management plan (DMP) will be created to describe all functions, processes, and specifications for data collection, cleaning and validation. The electronic CRFs (eCRFs) will include programmable edits to obtain immediate feedback if data are missing, out of range, illogical or potentially erroneous. These rules may encompass simple checks such as range validation or presence/absence of data, or complex cross-form verifications such as lab result deviations across visits. Concurrent manual data review may be performed based on parameters dictated by the DMP. Ad hoc queries to the sites may be generated and followed up for resolution. A source data quality audit may be initiated to ensure that the data in the database is accurate. Source data verification (SDV) will be performed at sites identified by a risk-based approach outlined in the monitoring plan, as needed.

The database will be housed in a physically and logically secure computer system maintained in accordance with a written security policy. The system will meet the standards of the International Committee on Harmonization guideline E6R1 regarding electronic study data handling. Patient confidentiality will be strictly maintained.

9.7 DATA ANALYSIS

9.7.1 Study Design

In this non-interventional study, cross-sectional data at study baseline and longitudinal follow-up data over 6 months will be collected for non-valvular AF patients with a current VKA therapy and subsequent initiation of Pradaxa[®] in Cohort A, and for newly diagnosed AF patients initiated on Pradaxa[®] or VKA in Cohort B.

Baseline data will be analyzed using a descriptive approach. Data from the longitudinal follow-up will be summarized descriptively. For Cohort A, mean differences in PACT-Q2 scores between assessments will be assessed using paired t-tests. For Cohort B, mean differences in PACT-Q2 scores between Pradaxa[®] and VKA patients will be assessed using propensity score matched analysis.

Due to the nature of this non-interventional study, there is no (confirmatory) hypothesis testing foreseen in a strict statistical sense. Analyses are descriptive in nature and confidence intervals and p-values from statistical models are used for exploratory purposes.

9.7.2 Planned Analysis

Analyses will be performed by Boehringer Ingelheim or Boehringer Ingelheim's designees. The main analysis population will consist of all eligible patients (i.e. all patients fulfilling all inclusion criteria and no exclusion criteria) from all participating countries.

Summary statistics for continuous variables will include the N, mean, standard deviation, minimum, Q1 (lower quartile), median, Q2 (upper quartile), and maximum value; tabulations of categorical variables will present all possible categories and will display the number of observations per category as well as percentages. Estimates will be presented with 95% confidence intervals.

Additional details of the planned analysis will be provided in the statistical and epidemiological analysis plan (SEAP).

9.7.3 Main analysis

Patient demographics and disease characteristics at baseline as described in section 9.3.2 will be summarized descriptively for all eligible patients in Cohort A and by treatment in Cohort B. This analysis may be repeated by additional relevant factors (e.g. country) that will be specified in the SEAP.

For Cohort A, the mean PACT-Q2 scores at the second and last assessments will be compared with the baseline assessment using paired t-tests.

For Cohort B, mean PACT-Q2 scores will be compared between Pradaxa[®] and VKA patients at the second and last assessments. Given the nature of this non-interventional study, patient in the two treatment groups may differ with regard to important baseline demographics and disease characteristics. When approximately half of the target sample size is reached, propensity scores that estimate the probabilities that patients would be initiated on Pradaxa[®] will be calculated using a logistic regression model including relevant baseline factors. The percentage of Pradaxa[®] and VKA patients that are matched with a 1:1 ratio and without replacement based on propensity scores will be calculated to assess the comparability of the two patient populations, and to estimate the loss of patients from the comparative analysis. Details of the propensity score model and the matching procedure, such as the choice of algorithm and caliper width will be described in the SEAP. If a sufficient percentage of matching (e.g. 90%) is achieved, the loss is considered minimal. If the percentage is considered not to be sufficient, the target sample size might be raised to increase the power of the comparative analysis.

For the final comparative analysis for Cohort B, Pradaxa[®] and VKA patients will be matched based on propensity scores following the same approach as described above. To assess the performance of the propensity score matching procedure, patient demographics and disease characteristics at baseline will be descriptively summarized again for the matched patients by treatment. Finally, the mean PACT-Q2 scores at each of the second and last assessments will be compared between the matched Pradaxa[®] and VKA patients using a paired t-test.

For both cohorts, the primary analyses will be based on the actual anticoagulation treatment the patients receive (i.e. “as treated” analysis). A patient is considered to have permanently discontinued initial anticoagulation treatment if other relevant anticoagulation treatment is initiated or otherwise dependent on the duration of treatment interruption (details will be provided in the SEAP). Patients who have permanently discontinued initial anticoagulation treatment at the time of an assessment will be excluded from all analyses where data from that assessment is included.

